4.1.13 Subject Compliance Monitoring

Study coordinators and physicians will inquire of the subjects to determine if they have escalated any current or initiated any new conservative therapies during the follow-up period.

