2.3 Outcome Variable

2.3.1 Primary Study Outcome Variable

Reduction in IPSS at 6-month follow-up.

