4.1.14 Criteria for Removal from Study

Subjects will be withdrawn from the study if a major complication occurs that prevents completion of PAE or the ability to complete the follow up visits.

Patients may also withdraw at any point at their discretion. Data will be included with an intent to treat analysis. Reasons for study withdrawal will be recorded.

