4.1.15 Follow-up for Withdrawn Subjects

If a subject withdraws from the study, any recorded data will still be included in the analysis. Subjects will only be replaced if they withdrew prior to undergoing PAE.

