4.2.2 Effectiveness Assessments

Technical success will be defined as bilateral prostatic artery embolization. This will be determined during the procedure. Clinical success will be defined as an IPSS score reported at the 6-month visit that is equal to or less than the pre-PAE baseline score. The size of the prostate will be measured by MRI at 6-month follow-up visit. IPSS, QoL, PVR and Qmax will be measured at 3, 6 and 12-month follow-ups.

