7.0 ADVERSE EVENTS (DRUGS- CONTRAST AGENTS)

7.1 Definitions

7.1.1 Adverse Event (AE)

An adverse event (AE) is any untoward medical occurrence (e.g., an abnormal laboratory finding, symptom, or disease temporally associated with the use of a drug) in a patient or clinical investigation subject administered a pharmaceutical product and which does not necessarily have a causal relationship with this treatment. An AE can therefore be any unfavorable and unintended sign (including an abnormal laboratory finding), symptom, or disease temporally associated with the use of a medicinal product, whether or not related to the medicinal product.

Hospitalization for elective surgery or routine clinical procedures that are not the result of an AE (e.g., surgical insertion of central line) need not be considered AEs and should not be recorded as an AE. Disease progression should not be recorded as an AE, unless it is attributable by the investigator to the study therapy.

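### No rule requires repeat PAE or prostate surgery after PAE to be recorded as re-treatment or handled in the analysis, so a post-procedure 6-month IPSS counts by default as a PAE result

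*Combined protocol and SAP*

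**What the plan says.** **What is asked in follow-up.** Section 4.1.13 has coordinators and physicians ask subjects to "determine if they have escalated any current or initiated any new conservative therapies during the follow-up period". Repeat PAE and prostate surgery are not conservative therapies. The Time and Events Table (4.3) schedules a medication history questionnaire at Visits 1, 2, 5 and 6, and AE assessment at Visits 3 to 6. Visit 7 has neither.

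**What is recorded as an event.** Section 7.1.1 excludes two things from AE recording. One is "Hospitalization for elective surgery or routine clinical procedures that are not the result of an AE". The other reads "Disease progression should not be recorded as an AE, unless it is attributable by the investigator to the study therapy". Section 9.3.1 separately has the co-PIs classify complications as major or minor on the CRF.

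**What is analysed.** The primary outcome in 2.3.1 is "Reduction in IPSS at 6-month follow-up". Section 4.2.2 states: "Clinical success will be defined as an IPSS score reported at the 6-month visit that is equal to or less than the pre-PAE baseline score". In 8.3 the model has terms for time and for whether medication had stopped by month 3. Its one sensitivity analysis drops men still on medication at month 3. None of these mentions a BPH procedure.

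**The concern.** Take a man whose PAE fails, who has prostate surgery or a second PAE at month 4, and who attends Visit 6. His IPSS then reflects the second procedure. So do his QoL, Qmax, PVR and prostate volume, which are the 6-month secondary outcomes in 2.3.2. All of them enter as results of the study PAE, and a treatment failure can be counted as a success.

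In a randomised trial, rescue can occur in both arms and may partly cancel. Here the reference is the same man's score on medication before PAE, which no later procedure can change. The stated aim (2.1, 8.1) is to compare PAE with medication, not PAE plus a further procedure. Readers of the report could not judge the effect either, because nothing obliges the study to count these men.

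**Working it through.** **1. Is there a rule anywhere?** For a procedure between PAE and Visit 6:

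| Place | What it covers | Does it handle a BPH procedure? |
|---|---|---|
| 4.1.13 | Conservative therapies | No |
| 4.1.10, 4.1.11, 4.3 | Medication questionnaire, AE assessment | Only if it surfaces as an AE |
| 7.1.1 | AE definition, with the two exclusions above | May exclude it |
| 9.3.1 | Complications on the CRF | Only if judged a complication |
| 4.1.14 | Withdrawal for major complication or by choice | No |
| 2.3.1, 4.2.2 | Primary outcome, clinical success | No condition |
| 8.3 | Model and sensitivity analysis | No term, no exclusion |

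AE or complication recording may capture some cases. An entry there would still leave the primary outcome and the success classification unchanged.

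**2. The plan's own figure.** Inputs from 8.2: SD 5.7 at both times, correlation 0.65, PAE decrease 9.23, medication decrease 6.6, alpha 0.025, 30 subjects, 20% dropout.
- SD of the paired difference = 5.7 × √(2 × (1 − 0.65)) = 4.77.
- Evaluable n = 30 × 0.8 = 24.
- Distance = (9.23 − 6.6) × 1.10 = 2.893.
- A one-sided paired t-test at 0.025 then has power 81.2%, which is the stated value.

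This calculation takes every 6-month score as reflecting PAE alone. It also uses a margin of 10% of 2.63 = 0.263 points, whereas 8.3 tests 10% of mean screening IPSS. That mismatch is a separate matter, and the 8.3 margin is used below.

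**3. Shift in the mean.** Assumption: k men are re-treated and each scores s points lower at 6 months than he would have without the procedure. Shift = k × s / n.

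| k | s = 5: n = 30 / n = 24 | s = 10: n = 30 / n = 24 | s = 15: n = 30 / n = 24 |
|---|---|---|---|
| 1 | 0.17 / 0.21 | 0.33 / 0.42 | 0.50 / 0.63 |
| 2 | 0.33 / 0.42 | 0.67 / 0.83 | 1.00 / 1.25 |
| 3 | 0.50 / 0.63 | 1.00 / 1.25 | 1.50 / 1.88 |

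**4. Against the margin.** No screening mean is given. If it is 15 to 20, the margin is 0.10 × 15 = 1.5 to 0.10 × 20 = 2.0 points. Two men at 10 points then use between 0.67/2.0 = 33% and 0.83/1.5 = 55% of it.

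**5. Effect on the test.** Simulation with the true mean difference exactly at the margin, SD of the difference 4.77, a simple paired t-test in place of the 8.3 model, n = 24, the k men with the worst change re-treated, and 40,000 runs per setting. Chance of a false non-inferiority finding at nominal one-sided 0.025:
- s = 5: about 0.05, 0.09 and 0.15 for k = 1, 2, 3.
- s = 10: about 0.08, 0.20 and 0.36.

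Taking the worst men makes this the unfavourable end of the illustration.

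**6. Clinical success.** Each re-treated man adds at most 1/30 = 3.3 to 1/24 = 4.2 percentage points, and only if he would otherwise have scored above baseline.

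**The case against.** **Some events would be seen.** AEs are assessed at months 3 and 6, and complications go on the CRF. The 7.1.1 exclusions sit in a section headed for drugs and contrast agents and have limits: surgery resulting from an AE is not excluded, nor is progression attributed to study therapy. This stands. A reader might infer that a re-treatment would be recorded nowhere, and the documents do not support that. They support only that no rule requires it to be recorded as re-treatment or handled in the analysis.

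**Keeping all observed scores is a recognised choice.** A treatment-policy analysis is legitimate. This also stands, but the plan does not state that choice for procedures, and even that analysis needs the events counted.

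**The intent-to-treat text.** A reader might infer that "Data will be included with an intent to treat analysis" (4.1.14) and "any recorded data will still be included in the analysis" (4.1.15) expressly keep a post-procedure score in the primary mean. Section 4.1.15 governs withdrawn subjects, and the 4.1.14 sentence follows one on voluntary withdrawal. A re-treated man who stays in the study is retained by the silence of 8.3. One who withdraws before Visit 6 becomes missing data instead.

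**The foreseen failure is covered.** Inability to stop medication is recorded at month 3, modelled, and given a sensitivity analysis. That analysis would also remove a later re-treated man if he was still on medication at month 3. It would not remove one who had stopped, and the primary analysis keeps both.

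**Clinical success is not a listed outcome.** It is absent from 2.3 and has no analysis in 8.3, so inflating it alters no planned test. It remains a defined measure of effectiveness that would misclassify these men.

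**Conclusion.** The point holds in this form. The primary outcome and the success definition, applied as written, credit the study PAE with the result of a later BPH procedure, for men re-treated before month 6 who attend Visit 6. Provided the procedure improves the score, the error runs only towards non-inferiority.

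Its size cannot be fixed from the documents, which give neither a re-treatment rate nor a screening mean. Under the stated assumptions it ranges from 0.17 points (one man, 5 points, n = 30) to 1.88 points (three men, 15 points, n = 24), against an assumed margin of 1.5 to 2.0. Only the largest combinations reach the margin. If no man is re-treated, results do not change.

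Three further inferences are not supported:
- The 7.9% acute urinary retention in 5.4 is a complication rate, not a re-treatment rate, so it does not predict how many men would be re-treated.
- Catheterisation is a poor example. Retention is a listed PAE complication that could surface as an AE, and an IPSS given with a catheter in place is hard to interpret rather than clearly better.
- No outcome listed in 2.3 is at 12 months, so a greater effect on 12-month results is not a finding about a planned endpoint.

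**What to change.** 1. **4.1.13:** replace 'conservative therapies' with 'any BPH treatment, drug or procedural'. Record type and date at Visits 5 and 6 on the existing medication form, and add the item at Visit 7, where that form is not now scheduled.
2. **4.2.2:** count a man who had a BPH procedure before the 6-month visit as not a clinical success.
3. **8.3:** report the number re-treated. Add a sensitivity analysis of the primary contrast that does not use post-procedure IPSS as a PAE outcome, for example by substituting the last pre-procedure score or the worst observed change. The all-observed-data analysis can remain primary if the sponsor prefers, provided that is stated.
4. **7.1.1:** clarify that the elective-surgery and disease-progression exclusions do not exempt BPH re-treatment from being recorded.

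The cost is protocol and SAP wording, one or two form items (including a new one at Visit 7) and one extra analysis. No visits are added. The reported success rate may be slightly lower.

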4.1.14 Criteria for Removal from Study

Subjects will be withdrawn from the study if a major complication occurs that prevents completion of PAE or the ability to complete the follow up visits.

Patients may also withdraw at any point at their discretion. Data will be included with an intent to treat analysis. Reasons for study withdrawal will be recorded.

4.1.15 Follow-up for Withdrawn Subjects

If a subject withdraws from the study, any recorded data will still be included in the analysis. Subjects will only be replaced if they withdrew prior to undergoing PAE.

4.2 Safety and Effectiveness Assessments

4.2.1 Safety Assessments

Subjects will be observed for several hours after PAE to monitor for immediate complications to include bleeding, infection and acute ischemia of the rectum and bladder. Subjects will be contacted by study personnel the day after PAE to inquire about delayed onset complications. The subjects will also be given a phone number that they can call to reach a nurse if they believe they have developed a complication of the procedure.

4.2.2 Effectiveness Assessments

Technical success will be defined as bilateral prostatic artery embolization. This will be determined during the procedure. Clinical success will be defined as an IPSS score reported at the 6-month visit that is equal to or less than the pre-PAE baseline score. The size of the prostate will be measured by MRI at 6-month follow-up visit. IPSS, QoL, PVR and Qmax will be measured at 3, 6 and 12-month follow-ups.

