3.1.3 Prostate gland measures \geq 50 grams measured by MRI, CT, or ultrasound

3.1.4 Currently taking BPH medications including either alpha blockers, 5-alpha reductase inhibitors or the combination of both for no less than 6 months

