4.1.4 Prior and Concomitant Therapy

The subjects will be required to have been on medical therapy for BPH for at least six months prior to undergoing PAE. Such medications include alpha blockers, 5-ARIs or combination therapy. The medication usage will be stopped by the 3 month visit in order to allow an adequate washout period for 5-ARI's prior to the 6 –month visit.

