4.1.10 Visit 5 - 3 Month Follow-Up

Subjects will return 90 +/- 14 days after PAE procedure to complete IPSS, and QOL questionnaires; to have Qmax and PVR measured; medication history questionnaires will be completed; and subjects will be evaluated for possible adverse events. It will be recorded if subjects are unable to hold medications at this time due to residual urinary symptoms. If an AE is suspected based on change in pain scores or functionality, an appropriate work-up will be performed.

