8.0 STATISTICAL CONSIDERATIONS

8.1 Study Design/Study Endpoints

The primary study aim is to determine if PAE is as effective as medication (non-inferiority) in reducing urinary symptoms due to BPH at 6 months.

This will be a single arm, non-blinded study of PAE using HydroPearl Beads in a small population with BPH to assess a clinically significant reduction in medications at 6 months. After IRB approval of a written informed consent and over, approximately a 24 month duration, N=30 subjects will be recruited. Only subjects ≥ 40 years will be screened for study recruitment. Clinical procedures and evaluations will consist of a preoperative screening assessment to determine if the potential study subject meets the inclusion and exclusion criteria, enrollment, surgical procedure for prostatic artery embolization (PAE), and follow-up visits at 24 hours, 1 week, 3, 6, & 12 months. An MRI will be performed after the 6-month visit in those patients who underwent embolization to detect a change in prostatic volume and perfusion and to exclude complication.

The study will be stopped if there is greater than one major complication (Grade D, E or F) as defined by the Society of Interventional Radiology Classification System for Complications by Outcome (29).

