8.3 Data Analysis Plans

A patient will be considered an evaluable study subject evaluable for data analysis per the following criteria, a written informed consent was obtained, he meets the inclusion and exclusion criteria, and received the PAE study procedure. All subjects with 12-month follow-up data will be included for analysis even if some follow up data is incomplete. Every attempt will be made to ensure that there is as

little missing data as possible including reminder phone calls and follow-up phone calls, if a subject misses a visit.

The primary aim is to demonstrate non-inferiority of PAE compared to medication with respect to the outcome measure IPSS. We assumed a non-inferiority margin of 10%, in line with the FDA's recommendations, since similar prior non-inferiority trials were unavailable. The null hypothesis states that in the target population mean IPSS is at least 10% greater at 6 months post-treatment than at baseline (pre-treatment). The alternative hypothesis will be that the mean IPSS at 6 months is less than or equal to 10% greater than the mean IPSS at screening.

To address this hypothesis we will implement a random effects linear model, modeling IPSS score as a function of time and the indicator of whether medication had stopped by the time of the 3-month follow-up. We will include an R-side compound symmetric random effect to account for patient-level correlation. We will compute the predicted mean and standard deviation(SD) of IPSS at screening and 6 months; the difference of the predicted mean IPSS score, defined as the mean IPSS at 6 months minus the mean IPSS at screening; and the SD of this difference. Point estimates of these values will be reported along with 95% confidence intervals for the mean difference.

A non-inferiority p-value <0.05 testing whether the difference in the predicted mean at screening is at least 10% greater than the predicted mean of IPSS at screening will be considered evidence against the null hypothesis of inferiority of PAE, compared to treatment. A non-inferiority p-value >0.05 will be considered inconclusive evidence against inferiority.

As a sensitivity analysis for the primary aim, we will repeat the same model outlined above after removing patients from the analysis who were still taking medications at the 3-month follow-up. Point estimates, confidence intervals, and p-values will be compared against those obtained in the primary analysis.

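### Clinical success in 4.2.2 does not require a man to be off BPH medication, so one who could not stop can be counted as a success if his 6-month IPSS is at or below his on-drug baseline.

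*Combined protocol and SAP*

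**What the plan says.** The definition in 4.2.2 is a single comparison: "Clinical success will be defined as an IPSS score reported at the 6-month visit that is equal to or less than the pre-PAE baseline". No other section adds a condition.

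The baseline is an on-drug score. Inclusion criterion 3.1.4 reads "Currently taking BPH medications including either alpha blockers, 5-alpha reductase inhibitors or the combination of both for no less than 6 months". The 6-month score is meant to be off-drug: 4.1.4 says "The medication usage will be stopped by the 3 month visit", and gives 5-ARI washout before the 6-month visit as the reason.

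The plan foresees that some men will not manage this. For the 3-month visit, 4.1.10 states: "It will be recorded if subjects are unable to hold medications at this time due to residual urinary symptoms". Section 4.1.13 has staff ask subjects to "determine if they have escalated any current or initiated any new conservative therapies during the follow-up period"; it does not mention procedures.

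In 8.3 the primary model for IPSS includes "the indicator of whether medication had stopped by the time of the 3-month follow-up", and a sensitivity analysis drops the men still on drugs at that visit. Section 8.1 describes the study as one "to assess a clinically significant reduction in medications at 6 months".

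**The concern.** A score no worse than an on-drug baseline shows that PAE has replaced the drug only if the drug has gone. Without that condition, an unchanged man on unchanged treatment meets the definition, although he is the plainest example of PAE not serving as a substitute. Substitution is the rationale in 1.2, and 2.1 frames the primary aim patient by patient. Section 4.2.2 is the only place where the protocol says what clinical success means for one patient.

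The same gap applies to a man who has another BPH procedure before month 6. His score would count, and nothing in 4.1.13 asks about the procedure.

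Any success rate reported from this definition would therefore mix men controlled by PAE alone with men controlled by their old drug, and possibly by a second procedure. A reader would naturally take it as the share for whom PAE did the work of the drug.

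**Working it through.** **Inputs.** From 8.2: SD of IPSS 5.7 at both times; correlation 0.65; decreases of 9.23 (PAE) and 6.6 (medication); 30 men, 20% dropout, alpha 0.025. Not in the documents: the share *f* of men who cannot stop, and the mean change *m* in those men. I assume *f* = 10, 20 or 30% and *m* = 0, and then vary *m*.

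**1. SD of the change.** 5.7 × √(2 × (1 − 0.65)) = 5.7 × 0.8367 = 4.77.

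**2. The plan's own figure.** With n = 30 × 0.8 = 24, a shift of (9.23 − 6.6) × 1.10 = 2.893, SD 4.77 and one-sided alpha 0.025, a paired t-test has power 0.812, matching the stated 81.2%. Taking the margin as 10% of the 2.63-point difference is my inference. I use the match only to support 4.77 as the SD behind the plan. The 81.2% concerns mean IPSS; the documents give no target or power for clinical success.

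**3. Chance that a man still on his drug is counted.** With a normal change, P = Φ(−m/4.77). With a half-point correction for whole-number scores, P = Φ((0.5 − m)/4.77).

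| Mean change *m* | P | P, half-point correction |
|---|---|---|
| +2 (worse) | 0.337 | 0.377 |
| 0 | 0.500 | 0.542 |
| −2.63 (better) | 0.709 | 0.744 |

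**4. Effect on the rate.** Inflation = *f* × P.

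| *f* | Points, P = 0.500 | Points, P = 0.542 | Men of 30, P = 0.542 |
|---|---|---|---|
| 10% | 5.0 | 5.4 | 1.6 |
| 20% | 10.0 | 10.8 | 3.3 |
| 30% | 15.0 | 16.3 | 4.9 |

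The result depends on *m*. At *f* = 20% without the correction, it is 0.2 × 0.337 = 6.7 points for *m* = +2 and 0.2 × 0.709 = 14.2 points for *m* = −2.63. If every man has mean change −2.63, the rate is 70.9% as written. It becomes 63.8, 56.7 or 49.7% when the 10, 20 or 30% still on drugs are not counted.

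**5. Does 8.3 repair it?** The covariate and the exclusion both enter the model for mean IPSS; neither reclassifies anyone under 4.2.2. Both use 3-month status, so a man who stops by month 3 and restarts before month 6 is coded as stopped and stays in the sensitivity analysis.

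**The case against.** The strongest reply is that little depends on this definition. Clinical success is not the primary outcome (2.3.1), is not among the five secondary outcomes (2.3.2) and has no analysis in section 8. No planned test uses it, and the definition does not itself claim to count men who came off medication. Continued drug use is not ignored either: 4.1.4 plans the stop, 8.3 adjusts for it and excludes men in a sensitivity analysis, and medication history is taken at 6 months (4.1.11, 4.3). All of that stands, and it limits the weight of the point. It does not change who is classed as a success.

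The size is also soft. Men who cannot stop are selected for residual symptoms, so zero mean change may be too kind or too harsh, and the documents give neither that mean nor the share.

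Four stronger readings are tempting, and the documents do not support them:

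- *Every man who could not stop is a success.* He is one only if his score is at or below baseline, about an even chance under the assumptions above.
- *Section 4.2.2 contradicts 8.1.* A symptom-based success definition and a medication-reduction aim can coexist. What is true is that no listed outcome measures the aim in 8.1, which is a separate gap.
- *The primary result is compromised in the same way.* The primary analysis concerns mean IPSS and deals with drug use in part.
- *Other procedures are known to inflate the rate.* This part rests on silence: no section gives a re-intervention rate or a rule for handling one.

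**Conclusion.** The point holds as a flaw in a descriptive measure. The definition omits the off-drug condition that gives its comparison meaning, the protocol itself expects men who will not meet that condition, and nothing in 8.3 corrects the classification. The inflation is about 5 to 16 percentage points if 10 to 30% of men cannot stop. That rests on the 8.2 SD and correlation, a normal change, an assumed mean change of zero in those men and an assumed share. No size can be put on the procedure part. The change is worth making before any success rate is reported, but no planned inference depends on it.

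**What to change.** In 4.2.2, define clinical success as all three of:

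- 6-month IPSS at or below the pre-PAE on-drug score;
- off BPH medication from the 3-month visit through Visit 6, taken from the Visit 5 and Visit 6 medication questionnaires;
- no other BPH procedure between PAE and Visit 6.

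The second condition follows the stop and washout already in 4.1.4 and changes no treatment. A shorter window, such as the one-month IPSS recall, would admit a man who stopped a 5-ARI only weeks before Visit 6. Check that the Visit 6 questionnaire covers the whole interval since Visit 5.

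Extend 4.1.13 to record BPH procedures as well as conservative therapies. I would not add a condition of no catheter since PAE. Section 5.4 cites acute urinary retention in 7.9% as a minor complication, about 2.4 of 30 men. If they were catheterised briefly (assumption), they would fail permanently whatever their 6-month state.

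Add to 8.3: n/N with an exact 95% confidence interval among men with a 6-month score, and a second figure counting missing scores as non-success. Both are needed because 20% dropout is 6 of 30 men, so the missing-data rule alone could move the rate by up to 20 points. Beside them, give the proportion off medication at 6 months, which supplies a measure for the aim in 8.1.

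The cost is a revised definition, one added question and a short descriptive table. The reported success rate is likely to be lower.
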